#### 9.1.1 Dose Escalation / De-escalation Decision Rule

	Number of patients Treated									
Decision Rule	1	2	3	4	5	6	7	8	9	
Escalate (or highest) if # DLT <=	0	0	0	0	1	1	1	1	2	
De-escalate (or lowest) if # DLT >=	1	1	2	2	2	3	3	3	4	
Eliminate (or stop) if # DLT >=			3	3	4	4	5	5	5	

Note: the next cohort will be treated at the current dose level if the criteria are not met for escalation/de-escalation rules.

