## Study Design

Describe and explain the study design (e.g., observational, secondary analysis, single/double blind, parallel, crossover, deception, etc.).

- Clinical Research: Indicate whether subjects will be randomized and whether subjects will receive any placebo.
- Community-Based Participatory Research: If you are conducting community-based participatory research (CBPR), describe
  strategies for involvement of community members in the design and implementation of the study, and dissemination of results from
  the study.
- Qualitative research: Indicate ranges where flexibility is needed, if a fixed interview transcript is not available, describe interview
  topics including the most sensitive potential questions.
- Research Repositories: If the purpose of this submission is to establish a Research Repository (bank, registry) and the material
  you plan to collect is already available from a commercial supplier, clinical lab, or established IRB approved research repository,
  provide scientific justification for establishing an additional repository collecting duplicate material. Describe the repository design
  and operating procedures. For relevant information to include, see the UK Research Registry Guidance.

This is a phase I dose escalation study with expansion cohort. Dose escalation will be determined by a Bayesian optimal interval design (BOIN) design [41]. Patients are enrolled in cohorts with 3 patients in each cohort. The primary endpoint is the DLT rate at each dose level. DLT rate is calculated as the total number of patients experienced DLTs at the current dose level divided by the total number and number of patients treated at the current dose level using the DLT. The calculation of DLT rate will only include DLT evaluable patients. The primary endpoints is to find the maximum tolerated dose.

-In the first cohort, a patient is considered evaluable if he completes 75% of doses. Patients that are not evaluable will be replaced.

- In the dose expansion cohort, a patient is considered evaluable if he completes 75% of the planned dosing.

Dose Escalation / De-escalation Decision Rule

Number of patients Treated
Decision Rule 1 2 3 4 5 6 7 8 9
Escalate (or highest) if # DLT >= 0 0 0 0 1 1 1 1 2
De-escalate (or lowest) if # DLT >= 1 1 2 2 2 3 3 3 4
Eliminate (or stop) if # DLT >= -- -- 3 3 4 4 5 5 5

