# 9. STATISTICAL CONSIDERATIONS

# 9.1 Study Design/Endpoints

This is a phase I dose escalation study with expansion cohort. Dose escalation will be determined by a Bayesian optimal interval (BOIN) design [41]. The target DLT rate is 30%. Patients are enrolled in cohorts with 3 patients in each cohort. Enrollment will be temporarily halted after the last patient of each cohort is enrolled until all current patients are DLT evaluable or withdrawn from the study. A patient will be considered DLT evaluable if he completes at least 75% of the planned dose of Epidiolex in the first 30 days of the treatment, unless the reason is due to toxicity.

The primary objective is to evaluate the acute toxicity and long-term safety and tolerability of Epidiolex (CBD) in patients with biochemically recurrent prostate cancer. Acute toxicity of Epidiolex is evaluated through DLT rate, which is calculated as the total number of patients experienced DLTs at a dose level divided by the total number of patients treated at the corresponding dose level. The calculation of DLT rate will only include DLT evaluable patients. Patients who are not DLT-evaluable will not be replaced for the current cohort and will not be included in the calculation of DLT rate. At the end of the dose escalation part of the study, we will use the dose escalation/de-escalation decision rules (see section 9.1.1) to decide the dose level for dose expansion cohort. If the current dose at the end of dose escalation is already the highest available dose, and the decision rules did not indicate de-escalation or elimination, the highest dose level is deemed as safe for acute toxicity; otherwise, the dose recommended by the decision rule is the estimated MTD.

Following dose-escalation, an expansion cohort will be enrolled to confirm safety for acute toxicity, evaluate long-term safety and tolerability and explore evidence of efficacy of the study treatment. Long-term safety and tolerability are evaluated through the summary statistics of adverse events occurred within the 90-day follow-up period in patients who received any amount of study drug. The study treatment is deemed as not safe for long-term tolerability if any of the following criteria are met:

- More than 40% of the patients treated at the dose level selected for expansion cohort experienced grade 3 or higher AEs that are possibly/probably/definitely related to study treatment

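### The dose-decision table is indexed by patients treated, while Section 9.1 limits the DLT rate to DLT-evaluable men; read literally, the label can only make a decision less cautious

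*Combined protocol and SAP*

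**What the plan says.** Section 9.1 defines the DLT rate as the number of men with a DLT at a dose, "divided by the total number of patients treated at the corresponding dose level". It then narrows this: "The calculation of DLT rate will only include DLT evaluable patients". On men who drop out of that count it says: "Patients who are not DLT-evaluable will not be replaced for the current cohort and will not be included in the calculation of DLT rate". A man is evaluable if he takes at least 75% of the planned dose in the first 30 days, or falls short because of toxicity.

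The table in Section 9.1.1 does not use a rate. It is entered by a DLT count and a column headed "Number of patients Treated", numbered 1 to 9. Its only note covers staying at the current dose and does not mention evaluability.

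The Study Design section of the IRB application repeats the header and also defines the rate over the "number of patients treated" at the current dose before restricting it to evaluable men. Unlike Section 9.1, it says that non-evaluable patients are replaced.

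Section 9.2 sizes escalation at up to 9 DLT-evaluable men and adds cohorts only if 3 or more of the first 9 are non-evaluable.

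**The concern.** The index of the decision rule and the denominator of the DLT rate are stated differently, and the plan allows them to diverge. With one or two non-evaluable men among the first nine, Section 9.1 replaces nobody and Section 9.2 triggers no extra cohort, so treated exceeds evaluable when a decision falls due. A site that follows the header then reads a column to the right of the one its DLT data support, which treats a man with no usable DLT information as DLT-free.

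Under Sections 9.1 and 9.3 this table drives every escalation decision, the MTD and the dose for the expansion cohort.

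**Working it through.** **Inputs.** Target DLT rate 30% and cohorts of 3 (Section 9.1); boundaries from Section 9.1.1. The documents do not state the BOIN interval or elimination settings. I assumed the standard ones: φ = 0.30, φ₁ = 0.6φ = 0.18, φ₂ = 1.4φ = 0.42, and elimination when Pr(p > 0.30) > 0.95 under a Beta(1,1) prior, from n = 3.

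**Step 1: reproduce the table.**

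- λₑ = ln[(1−φ₁)/(1−φ)] / ln[φ(1−φ₁)/(φ₁(1−φ))] = ln(0.82/0.70) / ln(0.246/0.126) = 0.2365
- λ_d = ln[(1−φ)/(1−φ₂)] / ln[φ₂(1−φ)/(φ(1−φ₂))] = ln(0.70/0.58) / ln(0.294/0.174) = 0.3585
- Escalate if DLTs ≤ floor(nλₑ): 0 0 0 0 1 1 1 1 2
- De-escalate if DLTs ≥ floor(nλ_d) + 1: 1 1 2 2 2 3 3 3 4
- Eliminate, n = 3 to 9: 3 3 4 4 5 5 5

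All 25 values match Section 9.1.1. The table therefore compares DLTs/n with 0.2365 and 0.3585, and its n is the denominator of the DLT rate.

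**Step 2: direction.** No boundary falls as n rises. For a fixed DLT count, moving to a column further right can leave the decision unchanged or make it less cautious, never more.

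**Step 3: decisions that differ with one non-evaluable man**, at the nominal looks, assuming that he contributes no DLT to the count:

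| Treated | Evaluable | DLTs | Evaluable column | Treated column |
|---|---|---|---|---|
| 3 | 2 | 1 | de-escalate | stay |
| 6 | 5 | 2 | de-escalate | stay |
| 9 | 8 | 2 | stay | escalate |
| 9 | 8 | 3 | de-escalate | stay |

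In the first row the observed rate is 1/2 = 0.50, above 0.3585.

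**Step 4: probability of a differing decision**, binomial in the evaluable men, at a true DLT rate of 0.30:

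- 3 treated: 2 × 0.3 × 0.7 = 0.42
- 6 treated: 10 × 0.3² × 0.7³ = 0.31
- 9 treated: 28 × 0.3² × 0.7⁶ + 56 × 0.3³ × 0.7⁵ = 0.296 + 0.254 = 0.55

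Over true rates of 0.10 to 0.50 the ranges are 0.18–0.50, 0.07–0.35 and 0.18–0.55. The look at 9 arises only if all three cohorts are treated at one dose.

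**Step 5: how often the situation arises.** The documents give no non-evaluable rate, so q is an assumption. The chance of at least one non-evaluable man in three is 1 − (1−q)³: 14%, 27% and 49% for q = 5%, 10% and 20%. For a first cohort with exactly one such man and a true DLT rate of 0.30, taking the two as independent, the chance of a differing decision is 3q(1−q)² × 0.42:

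- q = 5%: 0.135 × 0.42 = 0.06
- q = 10%: 0.243 × 0.42 = 0.10
- q = 20%: 0.384 × 0.42 = 0.16

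**Step 6: if the man is replaced**, as the IRB application says, the pairs become 4 treated/3 evaluable and 7/6. At 4/3 no decision differs. At 7/6 only 4 DLTs matter (eliminate against de-escalate), with probability 15 × 0.3⁴ × 0.7² = 0.06. The size of the problem therefore depends on which replacement statement applies.

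**The case against.** The strongest reply is that the flip depends on reading one header against the body text. Section 9.1 itself uses treated loosely and restricts it in the next sentence, so the header can carry the same restriction. Section 9.2 counts escalation in evaluable men up to 9, where the table ends, and the boundaries reproduce as DLTs/n. On that reading nothing changes. This stands as evidence of intent, and the boundaries are not in question.

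It does not settle the wording. The restriction is written for the rate, and no sentence applies it to the table's columns. Elsewhere in Section 9.1 the long-term safety assessment covers men who received any amount of drug, and its criterion refers to patients treated at the expansion dose. A literal reading of the header is therefore reasonable.

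A reader might also infer that every non-evaluable man makes the table less cautious. He does not: at 2 treated/1 evaluable, 4/3 and 8/7 no decision changes, and elsewhere only certain DLT counts matter. Nor is a raw cell count a risk. With 3, 6 or 9 treated and one or two non-evaluable, 10 of 33 combinations differ, all less cautious under the treated column. But the 33 are not equally likely, and 6 of the 10 need two non-evaluable men at one dose.

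**Conclusion.** The table's index is wrong as written: it conflicts with the denominator that Section 9.1 sets. The boundaries are correct, and the intended index was probably DLT-evaluable men. The documents do not support the stronger inference that the rule is miscalculated or that decisions will in fact be less cautious; that happens only if the header is applied literally.

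If it is, the error runs in one direction. Without replacement, and given one non-evaluable man, it is not small near the target: the Step 4 probabilities are 0.31 to 0.55 at a true rate of 30%. They rest on the 9.1.1 boundaries and binomial DLT counts. The claim that n is the rate denominator also uses the assumed BOIN settings, which match every boundary. How often a non-evaluable man occurs is unknown from the documents.

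**What to change.** - In Section 9.1.1 and in the Study Design section of the IRB application, relabel the column header as *Number of DLT-evaluable patients at the current dose level*.
- In both the Section 9.1 and the Study Design definitions of the DLT rate, change the denominator to DLT-evaluable patients at that dose level. The table, the rate and its confidence interval in Section 9.3 then share one denominator.
- Reconcile Section 9.1 (non-evaluable men not replaced) with Study Design (replaced).
- While editing the Study Design copy, reconcile its escalation row with Section 9.1.1: the inequality signs differ.

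The cost is wording in two places, with no change to the thresholds. The table already has columns for cohorts left incomplete by a non-evaluable man. The small downside is that some of those cohorts will get a more cautious decision than the literal header would give.

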## 9.1.2 Secondary and Correlative Endpoints

The secondary endpoints include change in serial PSA, PSA velocity and testosterone levels from baseline

Study ID: MCC-19-GU-74 Version Date: 15SEPT2020

throughout the treatment period as an indication of biochemical response and health-related quality of life (as assessed by the EORTC QLQ-C30 and QLQ-PR25).

The correlative endpoint includes CBD receptor 1 and 2 expression levels.

# 9.2 Sample Size/Accrual Rate

We plan to enroll up to 9 DLT evaluable patients for dose escalation. If 3 or more of the first 9 patients are not evaluable for DLT, additional cohort(s) will be enrolled to ensure at least 9 DLT evaluable patients for dose escalation. Once we have established the highest tolerated dose is deemed as acceptable for acute toxicity or estimated the MTD, we will begin treating 6 to 9 more patients in an expansion cohort to confirm safety for acute toxicity, evaluate long-term tolerability and explore evidence of efficacy of the study treatment. The number of patients to be enrolled in expansion cohort depends on the DLT rate during the dose escalation part of the study. The total planned sample size for this study is 18 (enrolled) patients with about 12 patients treated at the MTD or the highest planned dose.

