## **Data and Safety Monitoring**

The IRB requires review and approval of data and safety monitoring plans for greater than minimal risk research or NIH-funded/FDA-regulated clinical investigations.

- If you are conducting greater than minimal risk research, or your clinical investigation is NIH-funded, describe your Data and Safety Monitoring Plan (DSMP). Click here for additional guidance on developing a Data and Safety Monitoring Plan.
- If this is a non-sponsored investigator-initiated protocol considered greater than minimal risk research, and if you are planning on
  using a Data and Safety Monitoring Board (DSMB) as part of your DSMP, click here for additional guidance for information to
  include with your IRB application.

The Principal Investigator has primary responsibility for monitoring the safe conduct of this study. Additionally, the Markey Cancer Center Data Safety and Monitoring Plan outlines oversight and monitoring of all cancer clinical trials. The Committee is responsible for reviewing data to identify patient safety and protocol compliance issues. The Markey Protocol Review Committee (PRC) assigns studies a DSMC review timeline based on the phase, origination of the study and known safety issues.

The members of the MCC DSMC consist of Medical Oncologists, a Pharmacist, a Nurse Manager, a Certified Clinical Research Professional and a Reporter. These members were selected based on their experience, reputation for objectivity, and knowledge of clinical trial methodology. At each meeting, the following data is reviewed by the MCC DSMC: treatment issues, serious adverse events (SAEs) per FDA definitions, dose levels, dose modifications, and responses as applicable.

The DSMC reviews the protocol to assure the following: progress of the trial and safety of participants; compliance with requirements for the reporting of adverse events; any actions resulting in a temporary or permanent suspension by the sponsor; and data accuracy and protocol compliance.

The DSMC, the Protocol Review Committee (PRC), the responsible disease-specific Clinical Care and Research Team (CCART) and/or the UK IRB are empowered to immediately suspend accrual to any study under its purview for any of the following: Failure to comply with AE/SAE reporting requirements; poor study enrollment; protocol violations or issues related to patient safety.

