- More than 30 % of the patients experienced grade 3 or higher CNS toxicity that are possibly/probably/definitely related to study treatment

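### Expansion opens and continues on DLT counts alone; the plan's own 90-day grade 3+ criteria have no assessment time and no consequence for accrual

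*Combined protocol and SAP*

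**What the plan says.** **Dose decisions.** Section 9.1 states "The target DLT rate is 30" per cent and "Patients are enrolled in cohorts with 3 patients in each cohort". A man is DLT evaluable if he "completes at least 75% of the planned dose of Epidiolex in the first 30 days of the treatment", unless toxicity is the reason he did not. The halt between cohorts lasts "until all current patients are DLT evaluable or withdrawn from the study". The table in 9.1.1 then selects the expansion dose, and 9.3 confirms that dose decisions and the MTD come from that table. Section 9.2 opens expansion on acute toxicity or an estimated MTD: "we will begin treating 6 to 9 more patients in an expansion cohort".

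**Long-term criteria.** Section 9.1 judges tolerability over 90 days in everyone who received any drug. The treatment fails if either limit is passed by events at least possibly related to it: "More than 40% of the patients treated at the dose level selected for expansion cohort experienced grade 3 or higher AEs", or "More than 30 % of the patients experienced grade 3 or higher CNS toxicity". The first counts everyone treated at the expansion dose, so escalation men at that dose are included. The second names no dose level. Section 9.3 adds only descriptive summaries. None of these sections gives a time of assessment or an effect on enrolment.

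**Monitoring.** The Data and Safety Monitoring section of the IRB application lists what the monitoring committee (DSMC) reviews: "treatment issues, serious adverse events (SAEs) per FDA definitions, dose levels, dose modifications, and responses as applicable". It lets the DSMC and three other bodies suspend accrual at once over patient safety, without a numeric trigger. The Research Procedures section schedules adverse-event evaluation, laboratory tests and a review of the individual's dose level at Days 30, 60 and 90.

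**The concern.** The plan defines what counts as not tolerable over 90 days but does not connect that definition to the decision that exposes 6 to 9 more men. By the time expansion opens, some escalation men may have data beyond Day 30. Those data are collected and count toward the final verdict, yet no rule requires anyone to look at them first. Nor is any check stated during expansion, even after enough events have occurred that the verdict can no longer change.

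The committee's listed data do not supply the missing count. The criteria count related grade 3+ events whether or not they are serious. The risk section expects transaminase elevation, fatigue and somnolence in more than 10 of 100 people. Such events can reach grade 3 without meeting the definition of an SAE.

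**Working it through.** **1. Reproduce the decision table.** Inputs: target φ = 0.30 (section 9.1); default BOIN settings φ1 = 0.6φ = 0.18 and φ2 = 1.4φ = 0.42 (assumed, not stated).

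- λe = ln[(1−φ1)/(1−φ)] / ln[φ(1−φ1)/(φ1(1−φ))] = 0.2365
- λd = ln[(1−φ)/(1−φ2)] / ln[φ2(1−φ)/(φ(1−φ2))] = 0.3585
- Escalate at or below floor(nλe). De-escalate at or above ceil(nλd). Eliminate if Pr(rate > 0.30) > 0.95 under a Beta(1,1) prior with n ≥ 3.

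At n = 6: floor(1.42) = 1 and ceil(2.15) = 3. All 27 cells of 9.1.1 match, counting the two blank ones. The table is sound for DLTs; late events are not an input to it.

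**2. A path to a breach within 9 escalation men.** 0/3 at a lower dose leads to escalation. At the next dose 1/3 means stay, and a second cohort with 1/3 gives 2/6. Two is above 1 and below 3, so the rule is stay and this dose becomes the estimated MTD. One related grade 3+ event after Day 30 in a third man gives (2 + 1)/6 = 50%, above 40%. This assumes that each DLT is a related grade 3+ event, because the DLT definition is not in the supplied text.

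**3. Could it be seen at opening?** Evaluability needs 75% of 30 days of dosing, 0.75 × 30 = 22.5, so the first cohort clears at about Day 23 to 30. If the second cohort is followed for 30 days, the first is then at about Day 53 to 60, or later with slow accrual. At opening, the third event must therefore come from the first cohort and fall before about Day 60. Otherwise it appears during expansion. If only 3 men were treated at the dose (3 + 9 = 12, which fits the plan's figure of about 12), almost all late data arrive during expansion.

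**4. Counts that fix the final verdict.** Smallest k with k/N above the limit:

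| Final N at the dose | over 40% | over 30% (CNS, if counted at that dose) |
|---|---|---|
| 9 (3 + 6) | 4 (44.4%) | 3 (33.3%) |
| 12 (3 + 9 or 6 + 6) | 5 (41.7%) | 4 (33.3%) |
| 15 (6 + 9) | 7 (46.7%; 6/15 is exactly 40%) | 5 (33.3%) |
| 18 (9 + 9) | 8 (44.4%) | 6 (33.3%) |

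**5. How often?** The documents give no event rates, so these are assumed: DLT probability p of 5–20%; late related grade 3+ probability q of 10–40% in men without a DLT; each DLT counted as such an event; Day 90 data complete. With d the de-escalation boundary and k the smallest count above 40%:

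P(not de-escalated and over 40%) = Σ from x = 0 to d−1 of C(n,x) pˣ(1−p)ⁿ⁻ˣ × P[Bin(n−x, q) ≥ k−x]

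For n = 3, p = 0.10, q = 0.30 (d = 2, k = 2): 0.729 × 0.216 + 0.243 × 0.51 = 0.157 + 0.124 = 0.281.

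| n at dose | p = 10%, q = 30% | whole assumed range |
|---|---|---|
| 3 | 28% | 5–43% |
| 6 | 38% | 4–59% |
| 9 | 43% | 3–70% |

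These figures include doses from which the table would escalate, and they need full Day 90 data. They describe how often DLT counts and the 90-day limit can disagree, not how often expansion would open at a dose already in breach.

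**6. False alarms from a check at opening.** With 6 men, P(3 or more) is 9.9% at a true related grade 3+ rate of 20% and 25.6% at 30%. For CNS, P(2 or more of 6) is 11.4% at 10% and 34.5% at 20%. With 3 men, one CNS event (33.3%) is enough: 27.1% at 10% and 48.8% at 20%.

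**The case against.** The best defence is that choosing the dose on early DLTs is the stated design, and that expansion exists partly to evaluate long-term tolerability, so the two criteria are its end-of-study verdict. That explains why they are not dose-finding rules. It does not explain why nothing follows once the verdict can no longer change.

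Several stronger readings are tempting but not supported:

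- *Late toxicity enters no dose decision at all.* The Day 30, 60 and 90 visits include individual dose review. The gap is in cohort and expansion decisions.
- *The committee sees only SAEs, or cannot act.* Its list also covers treatment issues, dose levels, dose modifications and responses, and accrual can be suspended for safety. What stands is that SAEs are the only adverse-event category listed and that no trigger is tied to the criteria.
- *Expansion will typically open at a dose already in breach.* With 3 men at the dose, few late data exist at opening.
- *One DLT in 6 plus two late events shows the same thing at any dose.* At 1/6 the table says escalate, so below the top dose expansion would go to the next level. That example works only at the highest dose.
- *Five of 12 and 4 of 12 are the stopping counts.* They hold only for a final 12.

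Only section 9 of the clinical protocol is supplied, and the IRB application refers to fuller adverse-event text and to an institutional monitoring plan. A link might be stated there. The 30-day DLT window is itself inferred from the evaluability rule.

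**Conclusion.** The concern holds in limited form, and the plan should be changed. In the supplied text, opening and continuing expansion depend on acute toxicity only, while the 90-day criteria have no assessment time and no effect on accrual. Up to 9 more men could be enrolled at a dose whose treated men already exceed the plan's own limit. One late event after 2/6 DLTs is enough (50% against 40%). Where 3 men preceded expansion, the breach would mostly emerge during it.

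The worked path rests on DLTs being related grade 3+ events and on no link being stated in unsupplied text. The frequencies in step 5 rest on assumed rates and span 3–70%, so they are illustrative. The counts in step 4 are exact for the N shown. An excess at opening is not a final failure: 3/6 can still finish at 4/12 = 33.3%.

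**What to change.** **Sections 9.1 and 9.2.**

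- Before expansion opens, and at stated points during it, tabulate by dose all related grade 3+ events and all related grade 3+ CNS toxicity to date, including Days 31–90.
- If an existing criterion is exceeded at opening at the dose to be expanded, refer that dose to the DSMC before further accrual. Label this an interim review trigger, not a verdict.
- During expansion, hold accrual for DSMC review once the count reaches the smallest number above 40% (or 30% for CNS) of the final planned number at that dose: 5 and 4 of 12, or 7 and 5 of 15.
- State the denominator of the CNS criterion: the expansion dose or all treated men. The CNS counts above assume the former.
- State who assesses the two criteria and when.

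**Data and Safety Monitoring.** Add DLTs and related grade 3+ events by dose level to the DSMC's review data, with a review timed to these decisions.

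**Cost.** Wording and a one-page table from data already collected. The referral at opening is a new interim step and can delay a dose whose true rate is acceptable: 10–26% of the time with 6 men at assumed true rates of 20–30%, and more often for CNS with 3 men. Because it prompts review only, the expected loss is a short accrual pause. The 40% and 30% limits stay as they are, and no dose or treatment rule changes.
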